We are uniquely positioned to carry out the proposed project. [name] is a physician specializing in occupational medicine, with an extensive history of NIH support. He established strong working relationships with employment and labor agencies throughout the country, including CTULA. [name] is an expert in addictions and reinforcement interventions. She has successfully integrated these treatments in the context of randomized trials and clinical care in settings throughout the country. Recently, Drs. [name] and [name] published two studies together (Byrne et al., 2013; [name] et al., in press a), and Drs. [name] and [name] have worked together for over 10 years. [name] is a health economist with experience estimating costs and benefits of treatments, and he and [name] have a 7-year history of collaboration (see biosketches).

We completed several directly related projects that suggest the proposed study is likely to yield the anticipated benefits. First, [name] and [name] (2013) provided 30 non-treatment seeking hazardous drinkers with a cellphone, breathalyzer and training on video-recording alcohol breath tests (BrACs). Participants received up to three phone calls/texts daily, indicating that a BrAC test was due within the hour. They were randomized to: modest compensation for submitting dated time-stamped BrAC videos regardless of results, or the same plus reinforcement for submitting on-time alcohol negative tests (<0.02 g/dl). On average, $88.6\% \pm 10.4\%$ of requested BrACs were submitted on time, with no differences in submission rates between groups. BrAC results correlated with self reports of drinking and drinking consequences, $p < .01$. Negative BrACs and longest periods of negative BrACs were significantly greater with reinforcement, with $87.1\% \pm 11.1\%$ vs $66.9\% \pm 19.1\%$ of BrACs testing negative in the reinforcement vs monitoring only conditions, and 16.8 ± 10.1 vs 5.9 ± 3.4 days of consecutive negative samples in the two respective conditions. Group by time interaction effects were significant for changes in severity of alcohol problems as assessed by the Drinker Inventory of Consequences and Addiction Severity Index-Alcohol subscale scores, with greater reductions over time in the reinforcement condition. These data suggest the feasibility and initial efficacy of cell phones with breathalyzers to reinforce reductions in alcohol use in non-treatment seeking hazardous drinkers.

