Timeline: Months 1-3 will be used for training, start-up efforts and pilots. We expect to randomize about 7-8 participants into the study each month in months 4-42. This rate of recruitment is feasible because over 500 unique clients receive services each month at CTULA, with an estimated 15-20% meeting all inclusion criteria (and $<15\%$ are expected to meet exclusion criteria). Given the number of clients served throughout this agency, we plan to limit recruitment to one or two of the employment agency sites, but can expand to other sites if needed. Recruiting more quickly would necessitate more study staff due to the number of intervention visits, and this rate is consistent with our substance abuse treatment studies. With this enrollment rate, all intervention should be completed by month 47 and final follow-ups by month 55, leaving 5 months for analyses and report writing.

Data Analysis: An important issue preceding analyses is to identify baseline differences between groups despite random assignment. Group differences that may relate to outcomes (e.g., psychiatric diagnoses, occupational or medical status, drinking severity, services received) will be used as covariates or fixed factors in analyses. All randomized participants will be included using intent-to-treat analyses. Four primary outcomes are determined a priori: longest duration of negative samples (LDNS), % negative BrACs, % days worked for pay, and time to job attainment. The first three are continuous variables that can be transformed if needed. Drinking outcomes rely primarily on objective indices (BrACs), with subjective reports supplementing objective indices, such that one can be considered drinking if either index is positive. For LDNS, missing BrACs will be considered to break a string of negative samples. For % negative BrACs and % days working, missing data will be considered missing (not impacting the denominator) in one analysis, and positive/not working in another to consider the range of possibilities. ANOVAs (or ANCOVAs) will be conducted for drinking data and % days employed, evaluating both short-term (BL to month 3) and longer-term (throughout follow-up) efficacy. Time to job attainment will be evaluated with Cox survivor analyses, including covariates if needed.

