The design includes four treatment groups, allowing for examination of three main contrasts. Aim #1 is to evaluate whether reinforcing negative BrACs reduces drinking. Contrast weights of +1 will be assigned to Groups B and D and weights of -1 to Groups A and C to evaluate differences in LDNS and % negative BrACs in those assigned to interventions reinforcing negative BrACs vs those not. Aim #2 is to assess if reinforcing job-related activities reduces time to job attainment and increases % days working. Contrast weights of +1 will be assigned to Groups C and D and -1 to Groups A and B. Aim #3 is to examine if reinforcing both negative BrACs and job activities produces synergistic effects in terms of primary drinking and employment outcomes. To test this hypothesis, we will assign contrast weights of +2 to Group D, +1 to Groups B and C and -3 to Group A.

Power analyses. Our studies reinforcing drug abstinence find Cohen's d effect sizes of 0.5 to ≥ 1.0 for substance use outcomes ([name] et al., 2000, 2004, 2005abc, 2006b, 2007a, 2010b, 2011a, 2012abc), and our pilot trial using cell phone recorded BrACs yielded an effect size of $d=0.52$ for LDNS and $d=0.62$ for % negative BrACs ([name] & [name], 2013). Our study reinforcing job activities and abstinence (Drebing et al., 2007) had an effect size of 0.47 in terms of increasing job acquisition and 0.49 for abstinence. We conservatively powered this study to detect the smallest of these effect sizes. Using a Type I error rate of $\alpha=.05$, a Type II error rate of $\beta=.20$, and power=0.80 (Cohen, 1988), 62 participants are needed to detect

an effect size of $d=0.47$ between conditions reinforcing a target behavior and conditions not reinforcing that behavior.

We expect a smaller, but still clinically meaningful, effect size of $f=.22$ when comparing across reinforcer conditions. With power 0.80, 64 participants/group can detect $f=.22$ using the 3-group contrast in Aim 3 (Cohen, 1988). To accommodate for missing data, we will randomize 280 participants in total (70/group).

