With 70 participants/group in a 2x2 design, we will be overpowered to detect main effects of reinforcing negative BrACs on alcohol outcomes, and main effects of reinforcing job-related activities on employment outcomes. Nevertheless, this sample size provides power to ascertain if the combined reinforcement intervention is most effective. It also allows detection of a small to medium effect size in determining if reinforcing one behavior can improve both alcohol and employment outcomes (e.g., Group B > A, and Group C > A) to isolate the simplest efficacious reinforcement approach. Moreover, it permits evaluation of secondary outcomes and exploratory analyses of moderators and mediation effects.

Secondary aims are to evaluate the impact of interventions on other drug use, and mental and physical health indices. These are continuous measures, with missing data likely. If no systematic differences in missing data are noted, hierarchical linear models (HLM; Gibbons et al., 1993) using MIXREG (Hedeker, 1993) will analyze differences between groups over time. These analyses have advantages over repeated measures ANOVA as they estimate missing data via model parameter estimates and use real time, rather than scheduled time, of assessments. The same contrasts outlined above will be used to evaluate the aims. Analyses will be conducted for both short-term (e.g., BL to M3, with up to 3 data points/participant: BL,M1,M3) and long-term effects (BL through M12, with up to 6 data points: BL,M1,3,6,9,12). Models will include factors for group (using contrasts above), time, and interaction of group by time. Analyses will ascertain whether the interventions impact areas of functioning beyond alcohol use and employment indices. For example, reinforcement interventions can reduce psychiatric symptoms and improve quality of life ([name] et al., 2007b, in press c).

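### If the pilot's unequal spreads carry over, an ordinary pooled-error ANOVA on the raw scale miscalibrates the C vs A comparison on drinking and, more mildly, the Aim 3 contrast; the plan names no safeguard

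*Combined protocol and SAP*

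**What the plan says.** **Method.** Under Data Analysis the plan states that "ANOVAs (or ANCOVAs) will be conducted for drinking data and % days employed". The drinking outcomes are LDNS and % negative BrACs. Of these two and % days worked, the same paragraph adds: "The first three are continuous variables that can be transformed if needed". It says nothing about when a transformation would be needed or which one would be used. No variance check, separate-variance test or robust standard error appears anywhere.

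**Contrasts.** Aim 1 sets Groups B and D against A and C. Aim 2 sets C and D against A and B. For Aim 3, "we will assign contrast weights of +2 to Group D, +1 to Groups B and C and -3 to Group A".

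**Pairwise comparisons.** The Power analyses section says that the sample size also serves for "determining if reinforcing one behavior can improve both alcohol and employment outcomes (e.g., Group B > A, and Group C > A". It does not say how these comparisons will be tested.

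**Pilot spread.** Preliminary studies describes a pilot that "provided 30 non-treatment seeking hazardous drinkers with a cellphone, breathalyzer" and training. It reports "16.8 ± 10.1 vs 5.9 ± 3.4 days of consecutive negative samples in the two respective conditions" (reinforced first), and negative-test percentages of 87.1 ± 11.1 with reinforcement and 66.9 ± 19.1 with monitoring only.

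**The concern.** An ordinary ANOVA contrast takes its standard error from one mean square pooled over all groups. That is harmless when the groups have similar spread, or when the contrast weights the more and less variable groups equally. In this trial the pilot suggests that spread depends on whether negative BrACs are reinforced, so A and C would share one SD, and B and D another. C vs A uses only the unreinforced pair but would borrow its error from all four groups. Aim 3 puts most of its squared weight on Group A.

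The C vs A comparison on alcohol outcomes is how the plan would learn whether reinforcing job activities alone also reduces drinking, and the Future directions section builds on that answer. A true null there is fully compatible with B and D having a different spread, because it concerns only A and C.

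**Working it through.** **The plan's own figures.** The plan gives no error rate for these tests beyond a nominal alpha of .05, with sidedness not stated; two-sided is used here. Its figure of 64 per group at f = .22 for Aim 3 was not reproduced (three groups with 2 df need 68), but nothing below depends on it.

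**Inputs.** n = 70 per group (Power analyses). From Preliminary studies, for A and C (s0) and for B and D (s1):
- % negative BrACs: s0 = 19.1, s1 = 11.1, ratio 1.72
- LDNS: s0 = 3.4, s1 = 10.1, ratio 2.97

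**Formulas.** For weights c and equal n:
- true variance = Σc²s² / n
- pooled variance = Σc² × mean(s²) / n
- R = true / pooled
- actual two-sided alpha ≈ 2 × [1 − Φ(1.96 / √R)]

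Mean s² is (364.81 + 123.21)/2 = 244.01 for % negative and (11.56 + 102.01)/2 = 56.785 for LDNS.

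**Aims 1 and 2, and B vs A.** The squared weights fall equally on the two SDs, so R = 1 and alpha stays at 5%.

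**C vs A.**
- % negative: R = 364.81/244.01 = 1.495, √R = 1.223, alpha ≈ 10.9%.
- LDNS: R = 11.56/56.785 = 0.204, √R = 0.451, alpha ≈ 0.001%.

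**Power, C vs A on LDNS, shift 0.47 × 3.4 = 1.6 days.** The pooled SE is √(2 × 56.785/70) = 1.27, so an observed difference of about 2.5 days is needed. The true SE is √(2 × 11.56/70) = 0.575. Pooled power ≈ Φ((1.6 − 2.5)/0.575) ≈ 6%. With separate variances, power ≈ Φ(1.6/0.575 − 1.96) ≈ 79%.

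**Aim 3.** Squared weights are A 9, B 1, C 1, D 4, total 15, so A and C carry 10 and B and D carry 5.
- % negative: R = (10 × 364.81 + 5 × 123.21)/(15 × 244.01) = 1.165; alpha ≈ 6.9%, coverage ≈ 93%.
- LDNS: R = (10 × 11.56 + 5 × 102.01)/(15 × 56.785) = 0.735; alpha ≈ 2.2%, coverage ≈ 98%.

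**Simulation check.** 200,000 normal trials at 70 per group:

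| Contrast | Outcome | Pooled | Welch-Satterthwaite |
|---|---|---|---|
| C vs A | % negative | 10.9% | 5.0% |
| C vs A | LDNS | below 0.01% | 5.1% |
| Aim 3 | % negative | 6.9% | 5.0% |
| Aim 3 | LDNS | 2.3% | 5.1% |

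**If a transformation is used** (delta method, pooled error kept):

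| Scale | SD ratio | Aim 3 alpha | C vs A alpha |
|---|---|---|---|
| log LDNS | 1.04 | 4.8% | 4.5% |
| logit % negative | 1.15 | 4.5% | 3.5% |
| arcsine-root % negative | 1.23 | 5.8% | 7.4% |

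**Uncertainty in the SD ratio.** The pilot split is not given. Assuming 15/15, the 95% intervals are 1.00 to 2.97 (% negative) and 1.72 to 5.13 (LDNS). At the lower LDNS limit, C vs A still runs at about 0.6%. For % negative, a ratio of 1.3 gives about 8.0%.

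**The case against.** Four replies carry weight.

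1. **Pooling is inferred.** The plan says ANOVA and names no error term. C vs A is not among its three main contrasts; it appears only as an example in the sample-size discussion. Run as a two-group test it would use only A and C, which share one assumed SD, and the problem would vanish. This stands, but the plan does not say so, and it would not repair Aim 3.

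2. **Transformation is allowed.** A log scale would nearly remove the LDNS problem, and a logit or arcsine-root scale would shrink the one on % negative BrACs. This stands in part. With no trigger and no named scale the choice is open, arcsine-root still leaves C vs A at 7.4%, and a log is undefined for a run of zero.

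3. **The Aim 3 decision would not change.** A reader might infer from the 6.9% and 2.2% that the Aim 3 conclusion is at risk of being wrong. The documents' figures do not support that. Unequal spread would probably accompany a real reinforcement effect. With C equal to A, and B and D each above A by the pilot difference, the contrast is 3 × 10.9 = 32.7 days against a pooled SE of √(15 × 56.785/70) = 3.49, so t ≈ 9.4. For % negative BrACs it is 3 × 20.2 = 60.6 against 7.23, t ≈ 8.4. What remains is mainly interval coverage.

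4. **The evidence is thin.** The pilot had 30 people, and the interval for the % negative ratio reaches equality. The ± figures are not labelled as SDs. With an equal split, however, only their ratio matters for the error rates, and it is the same whether they are SDs or standard errors.

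**Conclusion.** The point holds conditionally. It rests on three assumptions: the pilot spreads carry over, the outcomes are analysed untransformed, and the four-group pooled error is used, including for C vs A. Under those, C vs A is the serious part. It is too liberal on % negative BrACs (about 10.9%) and nearly unable to reject on LDNS (about 6% power against 79%), so two primary drinking outcomes would be distorted in opposite directions on one question. For Aim 3 the effect is modest: coverage of about 93% and 98%.

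A reader might infer that the plan's primary tests in general carry wrong error rates. They do not: Aims 1 and 2 and B vs A keep 5% at equal n. Nor do the documents show any problem for % days worked, for which no SD is given, and the calculation does not bear on the Cox analysis of time to job attainment. The defect is an unspecified choice where the plan's own pilot gives reason to specify one.

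**What to change.** Keep the groups, contrast weights and sample size. Add one sentence to Data Analysis: all contrasts and pairwise comparisons on LDNS and % negative BrACs will use separate-variance standard errors, Welch-Satterthwaite when there are no covariates and HC3 when an ANCOVA is fitted. Name C vs A and B vs A there, so that their test is fixed too. Apply the same rule to % days worked only as a precaution.

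If a transformation is preferred for either drinking outcome, name it in advance and say how zero runs, or 0% and 100% values, will be handled; the separate-variance rule can still apply on that scale.

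The cost is one sentence and one software option, with a negligible loss of power if the variances prove equal. The simulation covered Welch-Satterthwaite only; HC3 was not simulated.

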job applications. Completing these activities relates to improved employment outcomes ([name] et al., in press a). Further, we have data from a randomized clinical trial showing that this reinforcement procedure enhances job-seeking and reduces time to job attainment in dual diagnosis veterans enrolled in a vocational training program (Drebog et al., 2007). Reinforcing job-seeking activities, therefore, may have direct benefits for the unemployed.

This study will examine methods to improve outcomes in unemployed hazardous drinkers referred to employment agencies, e.g. the Connecticut United Labor Agency (CTULA), the largest agency in the state that assists displaced workers. All participants will receive unemployment services plus alcohol monitoring, and some will be reinforced for abstaining from alcohol and/or participating in job-seeking activities. Primary aims are:

1. To assess the efficacy of reinforcing negative breathalyzer samples in the natural environment. Interventions that reinforce submission of negative breathalyzer samples are expected to decrease drinking and drinking-related adverse consequences relative to those that do not.
2. To determine whether reinforcing job-seeking activities enhances attainment of employment. Participants who receive reinforcement for completing job-seeking activities are expected to achieve earlier and higher rates of employment than those who are not reinforced for engaging in job-related activities.
3. To examine if a combined intervention results in the best outcomes. Those reinforced for both alcohol negative breath samples and job-seeking activities are expected to achieve the most benefits in both alcohol and employment domains.

The project will also evaluate the impact of the reinforcement interventions on secondary outcomes including psychiatric symptoms and health measures. Moderators and mediators of effects will be evaluated, with the expectations that heavier drinkers will experience poorer employment outcomes overall, and changes in drinking may mediate effects on finding employment and maintaining it long-term.

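### The Aim 3 contrast, used on its own, tests neither synergy nor whether the combined arm beats each single-reinforcer arm

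*Combined protocol and SAP*

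**What the plan says.** The Data Analysis section describes the four-group design as "allowing for examination of three main contrasts", one for each aim. Aim 1 sets B and D (+1) against A and C (−1), and Aim 2 sets C and D (+1) against A and B (−1). For the third, "Aim #3 is to examine if reinforcing both negative BrACs and job activities produces synergistic effects" on the primary drinking and employment outcomes, and the plan will "assign contrast weights of +2 to Group D, +1 to Groups B and C and -3 to Group A". The primary models are separate analyses: "ANOVAs (or ANCOVAs) will be conducted for drinking data and % days employed", with Cox regression for time to job attainment.

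Other sections word Aim 3 differently. Specific aims has "To examine if a combined intervention results in the best outcomes". The power text says "this sample size provides power to ascertain if the combined reinforcement intervention is most effective" and bases 64 per group at f = .22 on a calculation "using the 3-group contrast in Aim 3". The Significance section speaks of additive effects and the Innovation section of interactive ones.

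For secondary outcomes, "Models will include factors for group (using contrasts above), time, and interaction of group by time". No section writes down a BrAC-by-job interaction contrast, or a comparison of D with B or of D with C. The only pairwise examples given are B over A and C over A.

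**The concern.** Aim 3 is a primary aim, and the plan's own decisions turn on it. The rationale for four conditions expects B and C each to help the behavior it reinforces, perhaps without helping the other. It would let later work concentrate on one reinforcer if one is enough. Future directions ties adoption of the dual intervention to its having the best outcomes and being cost-effective. The Aim 3 test therefore has to separate three situations: the combination exceeds the sum of its parts, the combination merely equals its better part, and only one part works. A contrast that sets B, C and D together against A reacts to all three.

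**Working it through.** **Inputs.** From the protocol: 70 per group, α = .05, d = 0.47, and the Aim 1–3 weights. Assumed: SD = 1, a two-sided test (sidedness is not stated), and the mean patterns below. Group order is A, B, C, D.

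**The plan's own Aim 3 figure.** For f = .22, a three-group F test on 2 df with 64 per group has noncentrality 0.22² × 192 = 9.29 and power 77.8%; 80% needs 68 per group. So 64 is not reproduced on that reading. The calculation also describes an omnibus test across three groups, not the four-group weights.

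**Step 1: zero-sum check.** −3 + 1 + 1 + 2 = +1. A contrast that does not sum to zero shifts with the overall mean, so I examined three repairs:
- A set to −4: (−4, 1, 1, 2)
- recentred: (−3.25, .75, .75, 1.75)
- B and C pooled as one group: (−3, .5, .5, 2)

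**Step 2: overlap with synergy.** The interaction vector is I = (1, −1, −1, 1). Its share of squared weight is (c·I)² / (4 c·c).
- A = −4: c·I = −4, c·c = 22, share 16/88 = .182
- recentred: c·I = −3, c·c = 14.75, share 9/59 = .153
- pooled: c·I = −2, c·c = 13.5, share 4/54 = .074

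The remaining .818, .847 and .926 lie on the Aim 1 and Aim 2 main effects. The sign on synergy is negative each time.

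**Step 3: rejection rates.** Noncentral t on 276 df, noncentrality c·μ / √(c·c/70). For A = −4 with only BrAC reinforcement working, c·μ = 0.47 + 2(0.47) = 1.41, SE = √(22/70) = 0.561, noncentrality 2.515, rejection 71%.

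| True means (A, B, C, D) | A = −4 | Recentred | Pooled | Interaction test, favourable direction |
|---|---|---|---|---|
| One reinforcer only (0, .47, 0, .47) | 71% | 72% | 76% | 2.5% |
| Plateau (0, .47, .47, .47) | 92% | 91% | 89% | <0.1% |
| D half as good (0, .47, .47, .235) | 71% | 68% | 57% | <0.1% |
| D has no effect (0, .47, .47, 0) | 39% | 33% | 19% | <0.1% |
| Additive (0, .47, .47, .94) | >99% | >99% | >99% | 2.5% |
| Pure synergy (0, 0, 0, .47) | 39% | 43% | 57% | 50% |

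Sensitivity for the one-reinforcer row: 36–40% at d = 0.30; 79–84% and 91–94% at the pilot's 0.52 and 0.62; 67–72% at 64 per group with d = 0.47.

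**Step 4: the pattern the plan expects.** Let each reinforcer help only its own outcome (drinking 0, d, 0, d; employment 0, 0, d, d), with one outcome per domain and outcome correlation 0 to 0.5. By simulation, the contrast is significant on at least one outcome 85–94% of the time and on both 50–63%, with no synergy on either.

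**Step 5: the three codes entered together.** Inverting the matrix of intercept and three codes gives an Aim 3 row proportional to (−1, 1, 1, −1). That is the interaction with its sign reversed, so a positive coefficient means antagonism. With A = −4 the Aim 1 row is (.125, −.125, −.625, .625), that is 0.625(D − C) − 0.125(B − A). When only BrAC reinforcement works it estimates 0.235 with SE 0.108, against SE 0.060 for the Aim 1 code used alone. Aim 1 power falls from 97% to 59% (52% with the raw or recentred code, 31% pooled). If D has half the effect of B and C, the true Aim 1 main effect is (0.47 − 0.235)/2 = +0.12 SD, yet the joint coefficient is significantly negative 48–66% of the time.

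**The case against.** The best defence is that the weights encode an expected ordering, A below B and C, with D on top. That is close to the aim as worded in Specific aims, and the word for synergy may be loose. The ordering is a fair hypothesis, but rejecting the null does not establish it: the contrast is significant about 90% of the time when B, C and D are identical.

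A second defence is joint entry, which the wording for the secondary models permits and which three codes for four groups would fit naturally. The Step 3 rates then do not apply. The Aim 3 coefficient must instead be read backwards, and Aims 1 and 2 lose power and, if an interaction exists, no longer estimate main effects. D is still not compared with B or C.

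Third, the power text refers to effects across reinforcer conditions, of which there are three, so the authors may have meant to compare D with B and C. The list of pairwise examples is also open-ended. That stands as a limit: the criticism is of the stated weights, and the missing comparisons may be a gap in specification.

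Fourth, the rates depend on scenario. At d = 0.30 the one-reinforcer rate is below one half. Step 4 assumes exactly zero cross-effects, whereas the plan hopes that less drinking will help employment. Two groups improve in the one-reinforcer pattern and one under pure synergy, so part of that gap is built in, and the pooled version slightly exceeds the interaction test under pure synergy (57% against 50%). All true, but a test of synergy should stay near its nominal error rate when there is no synergy, and this one does not. The non-zero sum may be only notation if B and C were meant to be pooled.

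**Conclusion.** The concern holds and should be fixed before analysis. Used as a stand-alone planned contrast, which is the natural reading for the primary outcomes, the Aim 3 weights mainly re-test the two main effects. With 70 per group, d = 0.47, unit SD and two-sided 5%, they reject 71–76% of the time with one active reinforcer, 89–92% on a plateau and 39–57% under pure synergy. A directional interaction test would claim synergy at most 2.5% of the time in each non-synergy case, per outcome. The exact rates depend on the effect size and on which zero-sum repair is used. The direction of the problem does not: in all three repairs the contrast rejects more often for one active reinforcer than for pure synergy at the plan's d. Joint entry changes the defect without removing it.

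**What to change.** 1. For synergy, test +1 D, −1 B, −1 C, +1 A on each primary outcome (the product term in the Cox model), and claim it only if the estimate is in the favourable direction.
2. Estimate Aims 1 and 2 with their own ±1 codes, never jointly with the present Aim 3 code. State this for the secondary-outcome models too.
3. To claim the combination is best on an outcome, require D to beat both B and C on that outcome. D over C on drinking plus D over B on employment supports only a gain in both domains from adding the second reinforcer, and should be worded that way.
4. If the present pattern is kept, make it sum to zero, say whether B and C are pooled, and call it a supportive ordered trend.
5. Use one wording of Aim 3 throughout, and restate its power for items 1 and 3; the f = .22 basis does not describe those tests.

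The cost is SAP text and a less comfortable power statement; no new data are needed.
- **Interaction:** SE = 2/√70 = 0.239; 80% power needs about 0.67 SD (0.70 at 64 per group), and power at 0.47 SD is about 50%.
- **D against one single arm at 0.47 SD:** 79% (75% at 64).
- **D beating both B and C by 0.47 SD on one outcome:** 68% (63% at 64). On one drinking and one employment outcome together: 46–49% (assumed outcome correlation 0 to 0.3).
- **Cox product term:** SE = √(4/(70p)), where p is the proportion finding a job. Taking p = .28 to .50 from the veterans' trial in Preliminary studies as an assumption, 80% power needs a ratio of hazard ratios of about 3.5 to 2.6, and 1.95 even if everyone finds work.

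### The Aim 3 weights do not test synergy or show that the combined arm is best, and the power figures around them need restating

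*Combined protocol and SAP*

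**What the plan says.** In Methods, Data Analysis, the third contrast is introduced as follows: "Aim #3 is to examine if reinforcing both negative BrACs and job activities produces synergistic effects" on the primary drinking and employment outcomes. To test it, "we will assign contrast weights of +2 to Group D, +1 to Groups B and C and -3 to Group A". The Specific aims section words the same aim differently: the combined arm is expected to do best in both domains. The contrasts are reused for the secondary outcomes in the hierarchical linear models.

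Under Power analyses, with alpha .05 and power .80, "62 participants are needed to detect" an effect of d=0.47. No sidedness is given, and nothing says whether 62 is per group or in total. Next: "We expect a smaller, but still clinically meaningful, effect size of $f=.22$ when comparing across reinforcer conditions", and "64 participants/group can detect $f=.22$ using the 3-group contrast in Aim 3". The trial randomizes 70 per group.

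The section then states that "we will be overpowered to detect main effects of reinforcing negative BrACs on alcohol outcomes" (and likewise for job reinforcement on employment), that "this sample size provides power to ascertain if the combined reinforcement intervention is most effective", and that single-arm comparisons serve to find out whether a lone reinforcer will "improve both alcohol and employment outcomes (e.g., Group B > A, and Group C > A) to isolate the simplest efficacious reinforcement approach". The sentence about the combined arm names no test, effect size or power value.

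**The concern.** Synergy in a 2×2 design means that D exceeds what B and C would give by simple addition. A weighted sum that sets A against everything else, with D counted double, can be large without any synergy and without D beating B or C. A significant Aim 3 result could then be reported as evidence for the combined intervention when one component does all the work. The Future directions section ties clinical adoption of the dual intervention to its giving the best outcomes and being cost-effective, so this reading matters.

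The weights themselves are also unclear, and the two sample-size figures beside them cannot be traced to a named test.

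**Working it through.** **1. The figure of 62.** Inputs from Power analyses: d=0.47, alpha .05, power .80.
- Two-sided: n = 2(1.960+0.842)²/0.47² = 15.70/0.2209 = 71.1, so 72 per compared group. The exact t calculation gives 73.
- One-sided: 2(1.645+0.842)²/0.2209 = 56.0. The exact t calculation gives 57.
- 62 is neither. At 62 per compared group, power is 74% two-sided and 83% one-sided.
- Each main effect compares two pooled arms, 140 vs 140 (128 vs 128 at 64 per group). Power at d=0.47 is 97% (96%).

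**2. The figure of 64 per group.** Input f=.22, noncentral F with noncentrality f²×N.

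| Test | n/group for 80% | Power at 64 | Power at 70 |
|---|---|---|---|
| 3 groups, omnibus (2 df) | 68 | 77.8% | 81.6% |
| 3 groups, 1 df | 55 | 85.8% | 88.7% |
| 4 groups, omnibus (3 df) | 58 | 84.7% | 88.0% |
| 4 groups, 1 df | 42 | 93.9% | 95.6% |

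The nearest match is a 3-group omnibus test. A weighted contrast has 1 df, and 64 is not the requirement for that.

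**3. The sum of the weights.** Over four group means, 2+1+1-3 = +1. If every mean equals m, the weighted sum is m, not zero. If B and C are pooled into one single-target group, 2+1-3 = 0. That is valid and would explain the 3-group label, but the plan does not say it.

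**4. What a valid version responds to.** There are two zero-sum versions:
- V1: D +2, B +1, C +1, A -4. Sum of squares 22; SE at 70 per group = SD×√(22/70) = 0.561 SD.
- V2 (B and C pooled): D +2, B +0.5, C +0.5, A -3. Sum of squares 13.5; SE = SD×√(13.5/70) = 0.439 SD.

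Power is from the noncentral t on 276 df, two-sided .05. Effects are in SD units above A and use the plan's own 0.47. The interaction is D-B-C+A.

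| Truth | Interaction | V1 value, power | V2 value, power |
|---|---|---|---|
| Only breath-test reinforcement works (B=D=0.47, C=0) | 0 | 1.41, 71% | 1.175, 76% |
| B=C=D=0.47 | -0.47 | 1.88, 92% | 1.41, 89% |
| B=C=0.47, D=0.235 | -0.705 | 1.41, 71% | 0.94, 57% |
| Only D works (0.47) | +0.47 | 0.94, 39% | 0.94, 57% |

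Only the last row is synergy. V1 is least sensitive there. V2 is no more sensitive there than when D is half as good as B and C.

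**5. Tests that do answer the questions.**
- Pairwise (D vs B, D vs C, and equally B vs A and C vs A): power at 0.47 SD is 75% at 64 per group and 79% at 70. The minimum detectable effect at 80% power is 0.50 and 0.48 SD.
- Interaction D-B-C+A: SE = SD×√(4/n). Power at an assumed 0.47 SD is 47% at 64 and 50% at 70. The minimum detectable effect is 0.70 and 0.67 SD.

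**The case against.** The strongest defense is that an ordered contrast is a recognized choice for the pattern D above B and C, above A, and that Specific aims asks for the best outcomes rather than synergy. It stands in part: the contrast may be kept as a test of overall ordering. But Data Analysis says it tests synergy, and even as an ordered contrast it is significant about nine times in ten when D adds nothing over B or C.

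Three stronger readings are tempting, and the documents do not support them.
- *The weights are simply invalid.* Used literally on four means they are. With every group at the pilot's monitoring-only mean of 5.9 days (SD 3.4), the SE is 3.4×√(15/70) = 1.57, and a nominal 5% test rejects 96% of the time. But the pooled reading is open. As a coded predictor in a model with an intercept, or in the Cox model, equal groups give a slope of zero, so this harm does not carry over to the hierarchical models or to time to job attainment.
- *The trial is underpowered because 62 is wrong.* It is not. The main effects use 128 to 140 per side, and the plan's description of them as overpowered is right.
- *64 per group falls short.* No shortfall is shown. Rounding of f could nearly account for it: a 3-group omnibus test at f=.2249 has 79.7% power at 64. At exactly .22, 70 per group gives 81.6%.

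It is also fair to say that the claim about the combined arm follows directly on the f=.22 statement, so a reader may take it to rest on the Aim 3 contrast. That contrast cannot show D to be best.

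**Conclusion.** The concern holds. Under either valid reading, a significant Aim 3 contrast would not establish synergy or that D is the most effective arm, and the same contrasts carry this limit into the secondary outcomes. The sum of +1 is an ambiguity to resolve, not proof of an invalid test. The faults in 62 and 64 are minor: the first does not affect Aims 1 and 2, and the second is a figure without a named test.

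The calculations assume continuous outcomes with a common SD, equal groups, two-sided .05 and no multiplicity adjustment. The 0.47 SD pairwise effect is the plan's own. Its use as the size of an interaction, and the patterns of means in the table, are assumptions. Power for time to job attainment is not covered, because the plan gives no event count or hazard ratio.

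**What to change.** 1. In the primary and secondary analyses, test synergy by D-B-C+A. Assess whether the combination is most effective by its added benefit on each outcome: D vs B for drinking and D vs C for employment. Report each with a confidence interval. If the ordered contrast is kept, use zero-sum weights, state whether B and C are pooled, and do not interpret it as synergy or as D being best.
2. Replace 62 with 73 per compared group, stated as two-sided. Give main-effect power as 96-97% at d=0.47 for the continuous outcomes, and say that power for the Cox outcome depends on the number of events.
3. Name the test, degrees of freedom and pattern of means behind 64 per group.
4. Qualify the claim about the combined arm with the detectable effects at 64 to 70 per group: 0.48-0.50 SD pairwise (79% power at 0.47 SD with 70), and 0.67-0.70 SD for the interaction (about 50% at an assumed 0.47 SD with 70). The pairwise figures also apply to B vs A and C vs A.

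Cost: no added participants. The analysis and power text is revised, and the stated power for Aim 3 becomes less favorable.
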